Official Title: Improving Care Coordination for Adolescents and Young Adults With Cancer: Implementing a Bridge Between Needs and Services

NCT04586127

IRB-Approved Date: 2/9/2021

PStudy Title: Improving care coordination for adolescents and young adults with cancer: implementing a bridge between needs and services

Principal Investigator: [name]

Co-investigator(s):

[name], Wake Forest School of Medicine

[name], MSW, LCSW, Lineberger Comprehensive Cancer Center

Sponsor or funding source: Departmental

Background, Rationale and Context

In the United States, many of the nearly 90,000 adolescents and young adults (AYAs) diagnosed with cancer each year do not receive services to address the full scope of needs they experience during and after cancer treatment. AYAs' unmet needs result in negative outcomes, including distress, poor health-related quality of life, and high physical symptom burden. The National Cancer Institute and Centers for Medicare and Medicaid Services increasingly advocate for the use of patient-reported outcome measures (PROMs) in practice to better address the needs of cancer patients. However, PROMs are unlikely to address patient needs if patients and providers find them difficult to use, or if they are not linked to available services and resources that will address identified needs. Indeed, such limitations have stymied the implementation of PROMs in routine cancer care and their effect on downstream patient outcomes (e.g., improved symptom burden, quality of life, experience of care). Identified to the providers of the patients and their effect on downstream patient outcomes (e.g., improved symptom burden, quality of life, experience of care).

To facilitate a systematic and patient-centered approach to delivering services and resources to address the unmet needs of adolescents and young adults (AYAs) with cancer, we developed in preliminary studies the AYA Needs Assessment & Service Bridge (AYA NA-SB). AYA NA-SB includes (1) a holistic PROM assessing AYAs' physical, psychosocial and practical needs and (2) a collection of referral pathways for connecting AYAs to services and resources based on the needs they report (see **Appendix A**). To optimize AYA NA-SB's usability (i.e., ease of use) and usefulness (i.e., link to services), promote cancer programs' receptivity to AYA NA-SB implementation, and anticipate implementation strategies needed to facilitate AYA NA-SB's successful implementation and sustainment, we conducted usability testing, an ethnographic user and contextual analysis, and iterative prototyping workshops with a multidisciplinary design team.

Our development process culminated in an intervention with high usability and usefulness, characteristics we expect to promote AYA NA-SB's successful implementation and achievement of desired outcomes; however, AYA NA-SB's implementation and efficacy remain untested. Thus, through this study, we will evaluate AYA NA-SB's implementation and establish proof-of-concept. To avoid creating a tool that is only applicable to its high-resource testing environment, I will also plan for AYA NA-SB's potential scale-up across diverse health systems serving AYAs with cancer.

Objectives

Aim 1. Assess the implementation of AYA NA-SB. I will pilot AYA NA-SB in the North Carolina Cancer Hospital (NCCH), with a primary focus on implementation outcomes.

Aim 2. Establish proof-of-concept for AYA NA-SB. I will use pilot data to generate preliminary evidence on the extent to which AYA NA-SB addresses AYAs' reported needs.

Aim 3. Plan for AYA NA-SB's scalability and sustainability in diverse health systems. I will conduct annual 60-minute semi-structured qualitative interviews with AYA providers and program leaders from approximately 8 health systems to proactively address challenges and prepare for future AYA NA-SB scale-up and sustainability.

Methods and Measures

Design

- Aim 1/2: Single-arm feasibility pilot
- Aim 3: qualitative interviews

Setting

Aim 1/2: I will pilot AYA NA-SB in the North Carolina Cancer Hospital (NCCH). NCCH is a public, National Cancer Institute-designated Comprehensive Cancer Center located in central North Carolina, in a relatively metropolitan area. At NCCH, around 450 individuals ages 15-30 are diagnosed each year. About one third of these patients are treated in pediatric oncology and the remainder in adult oncology. NCCH's AYA program was established in 2015 with funding from a local nonprofit organization, the BeLoud Sophie Foundation. This funding was initially allocated towards hiring one fulltime employee (a social worker/program director) to provide AYA-specific care at NCCH. Since 2015, the program has evolved, hiring new AYA-specific staff members (e.g., nurse practitioner, fertility counselor) and expanding program activities and reach.

Aim 3: I will conduct interviews with providers and program leaders from AYA programs around the country.

Subjects selection criteria

• Inclusion Criteria

Aim 1/2: AYAs with cancer ages 18 through 39 currently in treatment at NCCH Aim 3: AYA providers and program leaders from around the country

• Exclusion Criteria

No exclusion criteria

• Sample Size

- Aim 1/2
 - \circ N=25-50 AYAs
 - o N=25/arm has been proposed as the minimum threshold of sample size for aims related to instrumentation. ¹⁸ Given that this is a single-arm pilot study, we have determined that a sample size between 25 and 50 is appropriate.
- Aim 3
 - N=8 AYA providers/ program leaders. Interviewees will be purposefully sampled such that
 they represent a range of health systems. As such, a sample size of 8 is expected to yield
 adequate data to meet the objectives of Aim 3.

Interventions and Interactions

Intervention (Aims 1, 2)

The intervention, AYA NA-SB, includes three components: (1) a needs assessment, (2) a map of referral pathways, and (3) implementation guidance (**Appendix A**).

Needs assessment. The needs assessment portion of AYA NA-SB is a 57-item PROM which includes nine domains: (1) information, (2) cancer care team, (3) physical health, (4) emotional health, (5) sexual and reproductive health, (6) health behaviors and wellness, (7) work and education, (8) peer support and programming, and (9) finances and everyday needs.

Referral pathways. Each domain of the needs assessment triggers a specific referral pathway. For example, needs reported in the 'sexual and reproductive health' domain trigger a referral to a fertility counselor or specialist while needs reported in the 'work and education' domain trigger a social worker visit. NCCH will tailor the map of referral pathways to their institution prior to the onset of data collection such that AYAs' needs are triaged to the appropriate parties at their institution.

Implementation guidance. Based on data collected during AYA NA-SB development, we compiled a list of potential implementation barriers and implementation strategies hypothesized to mitigate them. Participating NCCH providers will be given this information to inform their own deployment of strategies. To enhance the real-world applicability of findings, the implementation strategies will not be explicitly prescribed to NCCH, but the strategies they use will be carefully documented to contextualize findings.

Instruments & procedure (Aims 1,2)

Provider training. Six weeks prior to the onset of data collection, participating NCCH providers will participate in a 3-hour group training to familiarize them with the intervention and pilot protocol. In addition to the implementation leader, additional relevant providers identified by the implementation leader will participate in this training.

During the first hour of the training, I will provide an overview of AYA NA-SB and its development as well as a detailed summary of the pilot protocol. During the second hour of the training, we will collaboratively identify appropriate referral pathway providers for each needs assessment domain, explicitly outlining the

processes needed to initiate these referral pathways. During the third hour, we will brainstorm potential implementation strategies that might be deployed to facilitate AYA NA-SB implementation.

Needs assessment administration. The needs assessment portion of AYA NA-SB will be administered to AYAs through a secure online survey platform, RedCAP, and will take approximately 15 minutes to complete. The survey link will be delivered to AYAs through a patient portal message from the implementation leader. AYAs will receive a \$15 incentive for completing the needs assessment.

Referral pathway initiation. Within seven calendar days of AYA NA-SB completion, the implementation leader will review completed needs assessments and, depending on AYAs' preferences indicated at the end of the needs assessment, will either (a) initiate appropriate referral pathways, or (b) provide a list of recommended referrals to AYAs. For each needs assessment reviewed, they will document these actions on a brief fidelity checklist which timestamps their completion of these tasks, documents the referral pathways selected, and gauges their confidence in selecting appropriate referral pathways (**Appendix B**). This process is expected to take less than 10 minutes/ needs assessment.

Postintervention AYA survey. One month following their completion of the needs assessment, I will engage AYA pilot participants in an online postintervention survey (**Appendix C**) assessing their perceptions of AYA NA-SB's feasibility, acceptability, and appropriateness. In addition to items assessing AYAs' perspectives of the needs assessment itself, this survey will solicit information about the follow-up care AYAs received in response to needs they reported in the needs assessment and whether they felt their needs were met (Aim 2). This survey will administered through RedCAP and will take approximately 15 minutes to complete. AYAs will receive a second \$15 incentive for completing the postintervention survey.

Postintervention provider interview. I will conduct a semi-structured interview with the implementation leader and other participating providers from NCCH after AYA NA-SB has been administered to a minimum of n=15 AYAs. The purpose of this 1-hour interview is to assess provider perceptions of the feasibility, acceptability, and appropriateness of AYA NA-SB and to elicit information about perceived implementation determinants and strategies deployed. Interviews will be recorded and transcribed for analysis. **Appendix D** contains the interview guide.

Activity	Provider Training	Needs assessment administration	Referral pathway initiation	Postintervention AYA survey	Postintervention provider interview
Time	0	+6 weeks	+7 weeks	+10 weeks	+10-15 weeks

Instruments & procedure (Aims 3)

I will conduct annual semi-structured qualitative interviews with AYA providers and program leaders from diverse health systems to proactively address challenges and prepare for future AYA NA-SB scale-up and sustainability.

An interview guide (**Appendix E**) was developed using domains and constructs from the Dynamic Sustainability Framework, which conceptualizes the dynamic relationship among interventions, practice settings, and broader systems over time. ¹⁹ During interviews, I will review pilot data with providers and ask them to consider how AYA NA-SB's implementation and outcomes might unfold similarly or differently in their health systems given their practice context (e.g., staffing, informational systems, culture) and broader context (e.g., policy, regulations, market forces).

I will conduct interviews via telephone at a time of participants' choosing. Interviews will last approximately 60 minutes. They will be recorded and transcribed for analysis.

Outcome Measure(s)

Variable	Definition	Measure	Participants	Data source				
Demographic/clinical variables (Aim 1, Aim 2)								
Demographics	Age; sex; race/ethnicity; healt	AYAs	Needs assessment					
Clinical	Cancer diagnosis; stage at dia	AYAs	Needs Assessment					
variables		_						
	Implementation measures (Aim 1)							
Feasibility	extent to which AYA NA-	Feasibility of Intervention Measure	AYAs	Postintervention				
	SB can be successfully used (FIM) ²⁰			AYA survey				

	in cancer programs		Providers	Postintervention provider interview
Acceptability	perception of whether AYA-NA-SB is agreeable,	Acceptability of Intervention Measure (AIM) ²⁰	AYAs	Postintervention AYA survey
	palatable, or satisfactory to users		Providers	Postintervention provider interview
Appropriateness	SB's fit, relevance, or Measure (IAM) ²⁰		AYAs	Postintervention AYA survey
	compatibility with the context in which it will be used		Providers	Postintervention provider interviews
Fidelity	the degree to which AYA NA-SB is implemented as intended	Proportion of needs assessment reviewed by provider within one week and referral pathways initiated	Providers	Fidelity checklist
Implementation determinants	Perceived barriers and facilitators to AYA NS-SB implementation	Qualitative analysis of perceived determinants based on CFIR constructs	Providers	Postintervention provider interview
Implementation strategies	Strategies deployed to facilitate AYA NA-SB implementation	Qualitative analysis of strategies used and their perceived level of influence	Providers	Postintervention provider interview
	Service	e and patient outcomes (Aim 2)		
AYA needs	variables(?)	crosstab with demographic/clinical	AYAs	Needs assessment
	Prevalence of needs by follow demographic/clinical variable	$\operatorname{ss}(?)$		
Services rendered	reported needs	ays initiated in response to AYAs'	Providers	Fidelity Checklist
	needs reported by AYAs	esources rendered in response to	AYAs	Postintervention AYA survey
Care coordination	The delivery of multidisciplinary services to address needs reported by AYAs	AYA's receipt of services/ resources from across disciplines to address reported needs within one month of needs assessment completion	AYAs	Postintervention AYA survey
Needs met	Extent to which services and resources received met reported needs	AYAs' perception of the degree to which their needs were adequately addressed during the study period	AYAs	Postintervention AYA survey

Analytical Plan

Aim1. I will report descriptive

statistics on demographic and clinical variables. I will also calculate descriptive statistics on all quantitative implementation outcomes. Index scores will be generated for each measure by calculating an unweighted average of items within each construct. Further, I will conduct bivariate analyses to assess whether implementation outcomes vary by demographic and clinical variables to ensure that AYA NA-SB is feasible, acceptable, and appropriate across patient characteristics.

Qualitative interview data will be analyzed using template analysis²¹ based on a priori themes (i.e., Proctor's model and CFIR constructs) but allowing for additional emergent themes. A peer and I will independently abstract data from interview transcriptions per Proctor outcomes and CFIR constructs and discuss discrepancies until consensus is reached. When necessary, a third party will be pulled in to resolve discrepant coding.

Aim 2. I will calculate descriptive statistics on AYAs' identified needs, reporting the prevalence of specific needs and needs within specific domains, as well as on services received. I will also calculate descriptive statistics on quantitative service and patient outcomes. I will conduct bivariate analyses to assess whether service and patient outcomes vary by demographic and clinical variables.

Aim 3. Interview data will be analyzed using template analysis²¹ of interview transcriptions based on a priori themes (i.e., domains of the Dynamic Sustainability Framework) but allowing for additional emergent themes. A peer and I will independently abstract data from interview transcriptions and discuss discrepancies until consensus is reached. When necessary, a third party will be pulled in to resolve discrepant coding.

Human Subjects Protection

Subject Recruitment Methods

Aim 1/2: AYAs will be recruited by the implementation leader who, during routine encounters with AYAs, will provide a brief description of the study objectives and a 1-page recruitment flyer with additional details (**Appendix F**). Additionally, they will receive a fact sheet containing all of the relevant information from the consent form template (**Appendix G**). The implementation leader will distribute the needs assessment link to AYAs interested in participating (via a secure patient portal message), following up with non-responders using Dillman's approach for maximizing survey response rates which includes initial contact, then follow-up with non-responders at 1, 3, and 7 weeks.²²

When recruiting AYAs, implementation leaders will prioritize achieving heterogeneity in terms of cancer type, gender/sex, and race/ethnicity. The implementation leader will not share the identity of AYAs interested in participating, even to members of the study team.

Aim 3: Four interviewees have already been identified: (1) Program Manager, Stanford AYA Cancer Program, (2) AYA Nurse Navigator, University Hospitals, (3) Program Coordinator, Bon Secours St. Francis Cancer Center, and (4) Patient Navigator, Fort Worth AYA Oncology Coalition. With expressed support from Teen Cancer America, an advocacy group that consults with AYA programs around the country, I will identify four additional key contacts (i.e., AYA providers) from diverse health systems. I will email these key contacts information about the study, following Dillman's approach for maximizing response rates which includes initial contact, then follow-up with non-responders at 1, 3, and 7 weeks.²² Key contacts will identify individuals within their institution who are best equipped to participate in these annual interviews.

Informed Consent

Aim 1/2: During recruitment, AYAs will receive from their provider a study fact sheet with all relevant consent form information (**Appendix G**). This will give them time to review and process this information prior to receiving the online link to the first survey. Additionally, this will remove any pressure they may feel to agree to participate as a result of their provider being present. Informed consent will then be obtained from AYAs on the first page of the web-based needs assessment and postintervention AYA survey (see screenshot, below). This waiver of documentation of consent is appropriate because (1) this research presents no more than minimal risk of harm to participants, and (2) this research involves no procedures for which written consent is normally required outside the research context. Additionally, we believe that this 2-stage consent process will alleviate any undue pressure that AYAs feel to participate. Finally, this 2-stage consent process provides some measure of privacy

protection to potential participants because, although their provider will be aware of the identity of potential participants during recruitment, this information will not be shared with the study team.

Today, we are asking you to complete a survey about your cancer needs.					
The purpose of this survey is to identify your needs so that the UNC AYA team can connect you to services and resources that address those needs.					
This survey is also part of a research study on AYAs needs. The answers you provide will be stored securely to protect your privacy and confidentiality.					
You will receive a \$15 gift card for completing this survey.					
 First, we will ask you some questions about yourself. Second, we will ask you about your cancer needs. Finally, we will ask you a couple of closing questions. 					
Please contact [name] at [contact] if you ha	ave any questions about this survey or research study.				
Thank you!					
By checking this box, I certify that I give my consent freely to participant in this study.	☐ I consent ☐ I do not consent [End Survey]				
* must provide value	T do not consent [End survey]				

Aim 3: Prior to interviews, Aim 3 participants will receive a fact sheet containing consent information (Appendix H). Verbal consent will be obtained at the beginning of telephone interviews with providers.

Confidentiality and Privacy

Confidentiality will be protected by collecting only information needed to assess study outcomes, minimizing to the fullest extent possible the collection of any information that could directly identify subjects, and maintaining all study information in a secure manner. To help ensure subject privacy and confidentiality, only a unique study identifier will appear on the data collection form. Any collected patient identifying information corresponding to the unique study identifier will be maintained on a linkage file, store separately from the data. The linkage file will be kept secure, with access limited to designated study personnel. Subject-identifying information will be destroyed one year after closure of the study by permanently deleting all files, leaving only an anonymous analytical data set. Data access will be limited to study staff. Data and records will be kept locked and secured, with any computer data password protected. No reference to any individual participant will appear in reports, presentations, or publications that may arise from the study.

Data and Safety Monitoring

The principal investigator will be responsible for the overall monitoring of the data and safety of study participants. The principal investigator will be assisted by other members of the study staff.

Reporting of Unanticipated Problems, Adverse Events or Deviations

Any unanticipated problems, serious and unexpected adverse events, deviations or protocol changes will be promptly reported by the principal investigator or designated member of the research team to the IRB and sponsor or appropriate government agency if appropriate.

References

- 1. Society AC. American Cancer Society Cancer Prevention and Early Detection Facts and Figures, Tables & Figures 2020. 2020.

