Appendix C: Postintervention AYA survey

Acceptability of Intervention Measure (AIM)

	Completely disagree	Disagree	Neither agree nor disagree	Agree	Completely agree
1. The needs assessment meets my approval.	①	2	3	4	(5)
2. The needs assessment is appealing to me.	①	2	3	4	(5)
3. I like the needs assessment.	①	2	3	4	(5)
4. I welcome the needs assessment.	①	2	3	4	(5)

Intervention Appropriateness Measure (IAM)

	Completely disagree	Disagree	Neither agree nor disagree	Agree	Completely agree
1. The needs assessment seems fitting.	①	2	3	4	(5)
2. The needs assessment seems suitable.	①	2	3	4	(5)
3. The needs assessment seems applicable.	①	2	3	4	(5)
4. The needs assessment seems like a good match.	①	2	3	4	(5)

Feasibility of Intervention Measure (FIM)

	Completely disagree	Disagree	Neither agree nor disagree	Agree	Completely agree
1. The needs assessment seems implementable.	①	2	3	4	(5)
2. The needs assessment seems possible.	①	2	3	4	(5)
3. The needs assessment seems doable.	①	2	3	4	(5)
4. The needs assessment seems easy to use.	①	2	3	4	(5)

Face validity/ content validity

	Completely disagree	Disagree	Neither agree nor disagree	Agree	Completely agree
1. The needs assessment helped me to communicate my needs.	1	2	3	4	(5)
2. The needs assessment was relevant to me.	①	2	3	4	(5)
3. The needs assessment included all needs that I was concerned about.	•	2	3	4	\$

Usability

e successive y					
	Completely disagree	Disagree	Neither agree nor disagree	Agree	Completely agree

1. I think that I would like to complete the needs assessment again.	①	2	3	(4)	(5)
2. I found the needs assessment too complicated.	①	2	3	4	(5)
3. I think the needs assessment was easy to complete.	①	2	3	4	(5)
4. I think I would need help to complete the needs assessment.	①	2	3	4	(5)
5. I felt very confident completing the needs assessment.	1	2	3	4	(5)

Usefulness

	Completely disagree	Disagree	Neither agree nor disagree	Agree	Completely agree
1. The needs assessment provided a helpful way for me to tell my doctors what I need.	①	2	3	4	(5)
2. I did use or would use services and resources offered to me by my doctors based on the needs I checked in the needs assessment.	•	2	3	4	⑤

Care coordination/Needs met

	Yes	No
1. I reported no needs on the needs assessment	① (skip to end)	©
2. I received follow-up care for the needs I reported (e.g., referrals, counseling, other services or resources)	0	② (skip to end)

3. Please indicate the type of follow-up care that you received. (check all that apply)

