(1) communication from my primary oncology team
(2) a phone call or visit from a social worker
(3) a phone call or visit from a nurse navigator
(4) A referral to a specialist (e.g., fertility counselor, nutritionist, physical therapist, etc.)
(5) educational materials
(6) other

	Completely disagree	Disagree	Neither agree nor disagree	Agree	Completely agree
4. The follow-up care I received addressed my needs.	①	2	3	4	(5)

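### Aim 2 is worded as what AYA NA-SB does, but its survey outcomes cannot separate care prompted by the assessment from care already under way

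*Combined protocol and SAP*

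**What the plan says.** Objectives, Aim 2, states: "I will use pilot data to generate preliminary evidence on the extent to which AYA NA-SB addresses AYAs' reported needs". Under Design, Aims 1 and 2 are a "Single-arm feasibility pilot", and the inclusion criterion is "AYAs with cancer ages 18 through 39 currently in treatment at NCCH". Setting adds that "NCCH's AYA program was established in 2015 with funding from a local nonprofit organization". The program began with a social worker who directs it and has since grown by "hiring new AYA-specific staff members (e.g., nurse practitioner, fertility counselor) and expanding program activities and reach". Interventions and Interactions names a fertility counselor or specialist and a social worker visit as examples of where referral pathways lead. Under Subject Recruitment Methods the implementation leader approaches patients "during routine encounters with AYAs". The same person later reviews each assessment and either starts referrals or gives the AYA a list of them.

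One month after the assessment, Appendix C item 2 asks for yes or no to "I received follow-up care for the needs I reported". Item 3 offers six types of care: "communication from my primary oncology team", then social worker contact, nurse navigator contact, specialist referral, educational materials and other. Item 4 asks, on a five-point scale, whether that care dealt with the AYA's needs.

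In the Outcome Measure(s) table, care coordination, needs met and one of the two services-rendered measures come from this survey. The other services-rendered measure comes from the fidelity checklist. Needs met is defined over the study period without regard to source. The Aim 2 analysis is descriptive, with bivariate comparisons by patient characteristics.

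**The concern.** The aim is about what the intervention does. The survey items are about what the patient received. The two coincide only if a patient with a reported need would have received nothing for it that month without AYA NA-SB, and the setting makes that doubtful. Patients on treatment are in contact with an oncology team, and NCCH already employs the kinds of staff to whom the pathways lead. A social worker visit that was already arranged and one triggered by the assessment produce the same tick in item 3.

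If the total is reported as proof of concept, usual care is read as the intervention's work. The figure also travels: in Aim 3 the pilot data are reviewed with providers from other health systems who are asked how results might unfold there. The protocol itself regards NCCH as high-resource, so a figure containing NCCH's usual care would be a poor guide for them.

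**Working it through.** **1. What each source can show.**

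| Source | Tied to a reported need? | Shows what prompted the care? | Shows when the care began? |
|---|---|---|---|
| Needs assessment (Appendix A) | Yes; separate responses for needs already met | No; it does not ask which services are in place | No |
| Fidelity checklist (Appendix B) | Yes, by need number | Yes, for pathways initiated | Date of initiation, not receipt |
| Appendix C items 2–3 | Item 2 yes, for needs as a whole | No | No |
| Appendix C item 4 | Through item 2 | No | No |

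Item 4 rates whatever care item 2 admitted, so it inherits the same gap. The checklist could narrow the gap, but the Analytical Plan does not say that checklist and survey will be linked.

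**2. Size.** The plan states no rate for follow-up, with or without AYA NA-SB, so there is no figure to reproduce. All rates below are assumptions. Among AYAs reporting at least one need, let *u* be the share who would report follow-up care for it within the month anyway, and *d* the share of the remainder reached through AYA NA-SB. Then

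observed = u + (1 − u)·d, and contribution of AYA NA-SB = observed − u.

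For an observed 80%:

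| u | Contribution (80% − u) | d = contribution / (1 − u) |
|---|---|---|
| 0% | 80 points | 80% |
| 20% | 60 points | 75% |
| 40% | 40 points | 67% |
| 60% | 20 points | 50% |
| 80% | 0 points | 0% |

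The planned data cannot tell these rows apart. Since u cannot be negative, reading the total as the contribution can only overstate it.

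**3. Sample size does not help.** The plan gives N = 25–50. Exact 95% intervals for an observed 80% are 59% to 93% at 20/25 and 66% to 90% at 40/50. These cover sampling error only; the 0-to-80-point range in step 2 stays the same at any N.

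**4. A powered comparator is out of reach.** Take an assumed 60% against 80%, two-sided 0.05, with pooled proportion 0.70. Here √(2 × 0.70 × 0.30) = 0.648 and √(0.24 + 0.16) = 0.632.

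- n per arm for 80% power = (1.96 × 0.648 + 0.842 × 0.632)² / 0.20² ≈ 81.2, so 82.
- Power at 25 per arm = Φ[(0.20 × √25 − 1.96 × 0.648) / 0.632] = Φ(−0.43) ≈ 33%.

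The workable remedy is therefore to trace the source and timing of care, not to add an arm.

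**The case against.** The strongest reply is that this is a feasibility pilot. Its primary focus is implementation, Aim 2 asks only for preliminary evidence, and no efficacy test is planned. Lack of attribution is inherent in one arm. That stands, and it limits the weight of the point. It does not explain why the survey omits an inexpensive question about whether care was already in place.

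The plan also has safeguards. Appendix A lets the AYA mark that help or information is sufficient, or that the team is already doing what is asked, so reported needs exclude those the patient considers met. The relevant *u* is therefore lower than the chance of any contact in a month. It need not be zero: a patient already seeing a social worker who wants more help still reports a need, and the continuing visits can be ticked as follow-up. Usefulness item 2 in Appendix C does refer to services offered because of the assessment, but it merges having used them with being willing to, so it cannot count care received.

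Four stronger readings are tempting, and the documents do not support them:

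- *The survey counts any contact with the hospital.* Item 2 is confined to care for the needs reported. Nor does the list of options in item 3 show that usual care is being counted, since a social worker visit is itself a named pathway.
- *Participants are all patients of the AYA program.* Eligibility requires treatment at NCCH, not program enrolment.
- *All Aim 2 outcomes would look favourable even if AYA NA-SB did nothing.* The checklist measure of services rendered counts pathways initiated, which usual care does not generate. For the survey measures the result depends on *u*: with no effect and u = 20%, the observed figure is 20%.
- *The reported figure rises as the true contribution falls.* This follows only if *d* is held fixed. At d = 30%, u = 20%, 40% and 60% give 44%, 58% and 72%, with 24, 18 and 12 points from AYA NA-SB. Nothing in the plan fixes *d*.

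**Conclusion.** The point holds in limited form. The survey-based services rendered, care coordination and needs met outcomes record care for reported needs whatever its source or start date. They cannot separate care prompted by AYA NA-SB from care already under way, and any resulting bias favours the intervention. The response options for needs already met and the fidelity checklist reduce the problem without removing it.

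The size cannot be stated from the documents. The range of 0 to 80 points for an observed 80% shows what the data leave open; it does not estimate the bias. The conclusion rests on one assumption: that some on-treatment AYAs who report a need are already receiving, or would anyway receive, a service of a type listed in item 3. The Setting section makes this plausible but does not quantify it. This is an inexpensive improvement to a pilot and does not call the design into question.

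**What to change.** 1. In Appendix C item 3, add to each ticked option: *Was this already in place before you completed the needs assessment? Yes/No.*
2. Link each survey to its fidelity checklist by assessment or study identifier; names are not needed. Report follow-up in three groups: already in place; new, with a corresponding pathway initiated or recommended; new, without one. The middle group must include AYAs who chose to receive a list of recommended referrals, or care that AYA NA-SB prompted will be classed as unmatched. As laid out, Appendix B has a field for pathways initiated and none for referrals recommended, so add a mark to tell them apart.
3. Base the Aim 2 proof-of-concept statement on new care, give total follow-up as a descriptive figure, and state that without a comparator even new care is not proof of effect.

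The cost is about one minute of survey time, one extra mark on the checklist, one linked tabulation and a less favourable headline figure. No additional patients or visits are needed. The matching will be approximate, because the survey's service types are broad and not need-specific, and the new item relies on one month's recall. The item has to be in the survey before it is fielded.
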